*Possible adaptive control algorithms:* We will develop adaptive control algorithms using the Medtronic Research Development Kit. Since control algorithms will be based on each subjects' personalized neural signatures of mood states, we cannot specify exact algorithms prior to obtaining recordings from RC+S. In general, we expect the controller to utilize spectral power from one or more frequency bands extracted from cortical and/or basal ganglia recordings. Our preliminary data suggest that theta (5-8hz), alpha (8-10 Hz) and beta (12-30 Hz) as possible biomarker of mood. The controller will be based on threshold crossings in one or more of these frequency ranges and will change stimulation current between a low-therapeutic level and a high-therapeutic level. For each proposed control algorithm, we will test the performance of the algorithm using an external RC+S and the RDK prior to implementing adaptive control in the patient.

*Safety of adaptive stimulation:* During adaptive stimulation, several safety features protect patients from the potential from uncomfortably high stimulation settings or from prolonged periods with clinically inadequate settings. Stimulation parameters that can be implemented by the control algorithm are preselected with clinicians to avoid the possibility of producing major stimulation-induced adverse effects. No possible combination of stimulation settings will exceed the upper charge density limit of 30 microcoulombs per centimeter squared per phase. Prior to home testing, patients will be instructed on how to exit adaptive mode at any time and turn off cortical stimulation should excessive discomfort occur if needed.

*Conclusion of study:* Formal data collection will be completed at 5 years post implantation. However, it is expected that patients will be followed for life in our clinic, as is the case for patients implanted with DBS devices that are unrelated to research. The cortical electrode would not be utilized after the formal data collection phase is complete, unless further studies are conceived and approved based on the data collected in the present study.

At study completion, should adaptive PFC stimulation mode prove efficacy for individual patients, and the patient requests use of adaptive mode; they may be set to adaptive mode either on a “compassionate use” basis, with appropriate clinical follow up, or they may be offered participation in further research protocols that may be developed

Should a serious adverse event occur that is thought to be related to the presence of the cortical electrode, such as focal seizure or motor weakness congruent with device localization, the cortical lead will be removed. Removal will be accomplished by re-opening the original frontal incision and grasping the lead at or just posterior to the burr hole originally used for placement, taking care not to dislodge the therapeutic DBS electrode. The end of battery life for Activa PC+S is expected to occur 2-4 years after placement, depending on the chronic therapeutic stimulation parameters (similar to the non-research sister device Activa PC that does not have a sensing function). When its battery approaches end of life, it is expected that the Activa PC+S device will be replaced, via the original chest incision, with the Medtronic Summit RC+S device or a standard Medtronic pulse generator. The Summit RC+S IPG may be recharged for up to 9 years after placement, depending on the chronic therapeutic stimulation parameters (similar to the non-research sister device Summit RC that does not have a sensing function). Following this period – the RCS will be replaced with a commercially available DBS device.

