## **3.0 Investigational Plan**

This is a single-center study of the neurophysiology of non-motor symptoms associated with Parkinson's disease with several goals: (1) define the electrophysiological correlates (potential biomarkers) of non-motor symptoms (i.e. abnormal oscillatory activity), (2) determine the stimulation parameters that can disrupt such abnormal oscillatory activity and reduce these symptoms, (3) integrate potential electrophysiological biomarker into a closed-loop DBS paradigm and into neurofeedback training.

In a cohort of 10 subjects, we will assess the feasibility of improving non-motor symptoms using closed-loop stimulation. Upon UCSF Institutional Review Board (IRB) approval of our investigational plan and protocol, we propose to conduct this study in two phases for each subject. In phase 1 (1-7 months), patients will undergo long-term recordings of brain signals from electrodes placed over the PFC and in the basal ganglia (subthalamic nucleus or globus pallidus) along with monitoring of the severity of their non-motor symptoms. Since non-motor symptoms may fluctuate spontaneously and in response to dopaminergic treatment or basal ganglia stimulation, neural data will be recorded at multiple time points, in medication on and off states as well as in stimulation on and off states. At each brain data recording session non-motor symptoms will be assessed. Brain signals and symptom assessments will then be analyzed in order to identify a neuronal correlate, a biomarker, of non-motor symptoms and determine how stimulation modulates this abnormal brain activity. In the latter part of phase I, the effects of acute and chronic open loop cortical stimulation will be assessed.

In phase 2 (8 months - 5 years), we will develop a closed-loop paradigm that will automatically determine stimulation settings that optimally reduce non-motor symptoms based on the biomarker identified in phase 1. Using that biomarker we will also train patients to voluntarily modulate these abnormal signals. Subjects will be asked to voluntarily minimize the aberrant signals as represented by the position of a cursor on a screen, while their non-motor symptoms are assessed

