The free ends of the cortical lead and DBS lead are then placed in a subgaleal pocket, created by blunt dissection in the ipsilateral parietal area. After induction of general anesthesia, the ipsilateral head, neck and chest are prepped and draped, and the free ends of the lead and ECoG strip are accessed via a new 2 cm incision in the ipsilateral parietal area. The two electrodes are then attached to an Activa PC+S placed in the ipsilateral pectoral area, via two lead extenders (Medtronic Model 37087) recommended by the manufacturer for use with PC+S. The lead extenders are tunneled subcutaneously between the parietal incision and a 5 cm incision over the pectoralis muscle, where a pocket is bluntly dissected for the Activa PC+S. The contralateral DBS lead will constitute a separate system that is attached to a standard Activa SC primary cell generator in the contralateral pectoral area (via a standard model 37086 lead extender), and will not be used for neurophysiology data collection. If the patient were not participating in research,

he/she would receive either one Activa PC dual channel generator, or two Activa SC single channel generators (one on each side).

**Figure 3.** Schematic of implanted hardware as seen from top of head. The cortical electrode (red) passes through same burr hole as the ipsilateral DBS lead, covers the prefrontal cortex and is anchored with a titanium mini-plate.

*Activa PC+S Data collection sessions:* Detailed in **Table 2**. During data collection we will record up to four bipolar channels, from the cortical and/or subcortical electrodes, for up to 30 minutes prior to a data download. Data download will then be performed non-invasively using the Medtronic model 8181 sensing programmer provided by Medtronic Inc., via a wand resting on the skin over the Activa PC+S device, while the patient seated comfortably in a chair.

*Behavioral states for Activa PC+S brain data collection:* For each recording session, data will be collected in two behavioral conditions: at rest seated in a chair and during computer-controlled tasks that gage mood, anxiety, or impulsivity.

*Medication state for Activa PC+S brain data collection:* At most study visits occurring between surgery and 3 months after surgery, Activa PC+S brain data will be collected in the on and off medication states. For study visits 2 through 6 recordings will be done in the medication on and off states, in either order depending on patients' symptoms and comfort.

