The off medication state is defined as 12 hours off all anti-Parkinsonian medications at baseline (prior surgery) then will be tailor to capture patient's low mood state. The on medication state is defined as 30-60 minutes after normal or "suprathreshold" dose of anti-parkinsonian medication (dose greater than that required to induce an on-state). At all visits after that, data will be collected on or off medication depending on patient's symptoms in each medication state.

*Stimulation states for Activa PC+S brain data collection:* At all visits, brain data will be collected without therapeutic subcortical stimulation that is used to control motor symptoms. Therefore, DBS might be turned off before starting the Activa PC+S recordings. At visits between 4 months and 10 months, the effect of open-loop PFC stimulation on non-motor symptom severity will be tested and used to develop closed-loop paradigms. Therefore, for each visit between 4 and 10 months, data will be recorded with and without open-loop PFC stimulation.

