*Patient activation of the brain recording function:* All data collection in the formal study visits described above will be initiated by the study staff. In addition to these data collections, the patient will be given the Intercept Patient Programmer, model 37441, and allowed to "mark" distinctive or more severe phases of non-motor symptoms at home on their own. For example, a patient with fluctuating anxiety will be instructed in the outpatient clinic how to mark the anxiety onset at home, and initiate a brief brain recording. Any brain data collected during these visits may be downloaded in the next clinic visit or by patient him or herself at home. If the patient is not comfortable downloading the data at home, with the patient's permission, arrangements can be made for the study staff to visit the patient's home for data downloads. Study staff may also arrange with patients to visit their homes to help with initiating data collection. Such visits will ensure that data collection is initiated correctly, and by completing downloading at home, will reduce time spent during formal study visits to the clinic. In PD, non-motor symptoms often occur at predictable times during the day that coincide with medication state, allowing study staff to schedule recordings or a home visit likely to coincide with these symptoms. Patients can, for example, initiate a recording before medication during acute anxiety or depression episodes, or after medication, when these symptoms have improved. The intercept patient programmer does not enable stimulation of the electrodes; it only enables recordings of the data and is thus safe for patients to use at-home after initial training with research staff.

**Nexus-D and E System Study:** Patients who have had the Activa PC+S device implanted for 12 months (Phase 1 of the study) will start Phase 2 of the study that utilizes the Nexus-D and E interface, which is capable of

implementing closed-loop paradigms and neurofeedback cognitive training. Patients will participate in phase 2 of the trial, between 13 and 24 months post implantation, involving five visits.

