## **9.0 Statistical Methods and Data Analysis**

LFP data will be analyzed using wide power-spectral analysis as well as analysis of specific frequency domains (i.e. in the delta, theta, alpha, beta, gamma bands). We will also examine region-specific coherence and cross-frequency coupling in addition to coherence between cortical and subcortical brain areas. Using a repeated measures ANOVA statistical analysis, summary statistics for power in relevant frequency bands, power changes, and magnitude of coupling and coherence will be compared at different time points, different DBS conditions (on and off), different medication states (on and off), in a repeated measures (within subjects) design. The small number of subjects is mitigated by the ability to study varying mood states longitudinally within each subject. We will assess the correlation between the severity of non-motor symptoms and brain physiology measures. Additionally, bootstrapping statistical applications (i.e. a Monte Carlo algorithm) and general linear mixed models can be utilized to investigate potential statistical effects, given the small sample size).

Since this is a pilot study of chronic cortical recording, the sample size is likely to be too small to provide definitive answers to all research questions. Based on this exploratory analysis, it is anticipated that the next phase of the study will focus on a subset of the research aims, with 10 subjects per group.

Sample size calculation: This is a pilot study of a novel chronic brain recording technique. The goals are to assess technique feasibility, to collect pilot data that will be used to frame more detailed hypothesis about DBS mechanisms, and (in the add-on study using Nexus-D and E) to explore potential strategies for therapeutic use of the Activa PC+S and Summit RC+S neural interface. Thus, there is no formal sample size calculation.

*Criteria for study success that would justify a larger subsequent trial:* This study will be considered to justify a larger subsequent trial if we can demonstrate:

- 1) Chronic LFP recording from the cortex, of adequate quality to assess signatures of non-motor symptoms
- 2) No permanent serious adverse events occur
- 3) Therapeutic benefit in non-motor symptoms produced by cortical stimulation (open loop or closed loop) or neurofeedback training.

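### The planned symptom–signal correlation has no medication term, so in patients whose symptoms fluctuate with medication it cannot separate a mood marker from a medication-state marker

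*Combined protocol and SAP*

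**What the plan says.** **Analysis (section 9.0).** The only statement that connects symptoms to signals is "We will assess the correlation between the severity of non-motor symptoms and brain physiology measures". It names no medication term, stratum or within-state restriction. Medication state is a factor in a repeated-measures ANOVA, but the outcomes there are power, coupling and coherence; symptom severity is not in that model. Mixed models are optional and have no stated terms: "general linear mixed models can be utilized to investigate potential statistical effects". On sample size the section argues that "The small number of subjects is mitigated by the ability to study varying mood states longitudinally within each subject".

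**Sampling (section 6.0).** Both states are recorded early: "For study visits 2 through 6 recordings will be done in the medication on and off states". After baseline the off state has no fixed length; it is "12 hours off all anti-Parkinsonian medications at baseline (prior surgery) then will be tailor to capture" the low mood state. For later visits, "At all visits after that, data will be collected on or off medication depending on" the patient's symptoms in each state; Table 2 leaves the state open at visits 7–10. At home, patients can "initiate a recording before medication during acute anxiety or depression episodes, or after medication, when these symptoms have improved".

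**Expected effects.** Section 3.0 says "non-motor symptoms may fluctuate spontaneously and in response to dopaminergic treatment or basal ganglia stimulation". Section 4.0 lists a 30% on-versus-off VAS improvement among the four qualifying symptom criteria. Hypothesis 2 in the Synopsis expects prefrontal signals to vary with medication state in patients whose non-motor symptoms fluctuate.

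**The concern.** By the plan's own account, medication can move both variables in the correlation, and the sampling ties low mood to the off state. If Hypothesis 2 is true, the Hypothesis 1 correlation can differ from zero with no mood–signal link within either state. The within-patient design does not help here, because medication varies within the patient.

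The result is used. The phase 1 signal is to trigger closed-loop stimulation and to drive neurofeedback (sections 3.0 and 6.0), and a cortical biomarker of depression and anxiety is criterion 8d for RC+S replacement (section 4.0). A controller built on a medication-state marker would follow the dose cycle. Criteria 8c and 8e and the blinded sham test limit the harm, but they test the benefit of stimulation, not what the signal tracks.

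**Working it through.** **Inputs.** From the documents: 10 patients; visits 2–6 in both states, so 5 × 2 = 10 recordings per patient if there is one per state. Section 9.0 gives no alpha, power or sample size calculation, so there is no figure to reproduce. Assumed: within-state SD of 1 for mood and signal, no link within a state, a fraction f of patients shifting in both, and off-versus-on shifts d_s (signal) and d_m (mood) as listed. The documents give no shifts.

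**Step 1: slope without a medication term.** A shifting patient adds 10·(d_s/2)(d_m/2) = 2.5·d_s·d_m to the cross-product and 2.5·d_m² to the mood sum of squares. Every patient adds 9 to the mood sum of squares. The expected slope is therefore about

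f·2.5·d_s·d_m / (9 + f·2.5·d_m²).

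| d_s/d_m | Half shift | All shift |
|---|---|---|
| 0.5/0.5 | 0.3125/9.3125 = 0.03 | 0.625/9.625 = 0.06 |
| 0.8/1.0 | 1.0/10.25 = 0.10 | 2.0/11.5 = 0.17 |
| 1/1 | 1.25/10.25 = 0.12 | 2.5/11.5 = 0.22 |
| 0.8/1.5 | 1.5/11.8125 = 0.13 | 3.0/14.625 = 0.21 |

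Simulation agrees (0.033, 0.098, 0.122, 0.129 and 0.063, 0.174, 0.219, 0.206). At a nominal 5%, pooled false positives are 6%, 15%, 21% and 26% if half shift, and 9%, 41%, 56% and 65% if all do. For one patient with 10 recordings they are 5%, 7%, 9% and 10%.

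**Step 2: form of the medication term.** With half shifting, one common medication term still leaves 5%, 8%, 9% and 11%. Patient-by-medication terms give about 5% throughout.

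**Step 3: why off/on terms alone are not enough.** With patient and patient-by-medication terms the mood sum of squares is about 100 − 20 = 80.

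- *Recovery trend.* Visits 2–6 run from day 1 to 2 months after surgery. Assume a shift of 1, 0.5, 0.25, 0, 0 SD over these visits in both mood and signal. Its sum of squares per patient and state is 1.3125 − 1.75²/5 = 0.70, so 0.70 × 2 × 10 = 14 in total. The spurious slope is 14/(80 + 14) = 0.15. Starting at 1.5 SD it is 31.5/111.5 = 0.28. False positives are about 27% and 75%. Visit terms restore about 5%.
- *Varying dopaminergic level within off.* Assume it adds v SD to both variables in the five shifting patients, with 5 × 4 = 20 degrees of freedom. The slope is 20v²/(80 + 20v²) = 0.06, 0.11 and 0.20 at v = 0.5, 0.7 and 1.0. False positives are about 8%, 17% and 43%. A dose-timing covariate restores about 5% if it captures that level.

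**Step 4: precision.** Four visit terms and one dose-timing term leave 75, with 74 residual degrees of freedom: half-width 1.99/√75 = 0.23, against 0.22 with patient-by-medication terms only and 0.20 unadjusted (0.8/1.0, half shifting). Power for a slope of 0.3 is about 72%. It falls to about 54% if tailoring narrows the off-state mood SD to 0.5. For one patient with a medication term, 2.36/√8 = 0.84, and about 0.9 on average in simulation; further terms widen it.

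**The case against.** **Hypothesis 1 does not claim independence from medication.** It says only that signals correlate with severity, and medication is a deliberate way to move symptoms. If dopamine acts on mood through this circuit, the across-state correlation is real and adjustment removes part of it. This stands: the adjusted estimate cannot be the only valid one, and zero is the right reference only for the within-state question.

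**The study is exploratory.** Section 9.0 sets no alpha and expects the sample to be too small for definitive answers. This stands as a limit on the error rates, which are illustrations. It does not answer the point, because the chosen signal is acted on.

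**Controllers are personalised.** Section 6.0 makes control algorithms patient-specific, and with 10 recordings the inflation there is small. This also stands. A reader might infer from the 41–65% figures that a false biomarker is likely. The documents do not support that: those figures need all 10 patients to shift in both variables, whereas fluctuation is one of four listed symptom criteria and Hypothesis 2 is confined to fluctuating patients.

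**Other data could help.** The ANOVA may show that a signal is medication-sensitive, visits 7–10 compare cortical stimulation off, on and off, and the blinded test keeps regular medication. These are partial safeguards. None is stated as an analysis of mood against signal within a medication state, and the blinded test is optional and comes after the marker is identified.

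**Conclusion.** The concern holds in a limited form. In patients whose symptoms fluctuate with medication, the stated correlation cannot distinguish a mood marker from a medication-state marker, and no section states an analysis that does. The bias needs medication to affect both mood and signal. Its size is unknown: about 0.03–0.13 SD per SD with half the patients shifting and 0.06–0.22 with all, under assumed shifts of 0.5–1.5 SD. Symptom-chosen states at visits 7–10 and home recordings are not in these figures.

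Two stronger readings are not supported. The plan does not show that the marker will be wrong. Nor does an association that weakens on adjustment show that a signal is unrelated to mood. It should be fixed because the remedy uses recordings already planned, and dose timing that is not logged may not be recoverable later.

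**What to change.** In section 9.0, for Hypothesis 1:

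- Fit a within-patient model of signal on patient-centred VAS to the visit 2–6 recordings. Include patient effects, patient-by-medication terms (or a random medication slope), visit (time since surgery) terms, and time since last dose.
- Log time since last dose at every recording.
- Report the across-state (unadjusted) and within-state (adjusted) associations side by side with 95% intervals.
- Call a signal a mood marker separable from medication state only where the within-state estimate supports it. Otherwise report it as associated with mood but not separated from medication state.
- For each patient's controller, report the same two associations as estimates with intervals, not as a test. With 10 recordings the medication term alone gives a half-width of about 0.9, so keep further terms few.

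**Cost.** SAP wording and one logged field. Intervals widen and power is modest, as in Step 4 of the working, and the within-state estimate will be imprecise where mood hardly varies within a state. The dose-timing term helps only as far as it captures dopaminergic level. Adjustment can remove mediated signal, which is why both estimates are reported. No change to medication rules, visits or recordings is proposed.

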Objectives	
In ten patients undergoing DBS implantation for PD, we will implant a subdural cortical electrode in addition to the DBS electrode, and connect these to a novel implantable pulse generator that can store / stream field potential data (Medtronic Activa PC+S, Medtronic Summit RC+S). At multiple time points post-implantation up to 5 years, in our clinic or patients' homes, cortical and subcortical signals will be recorded. Data will be collected while patients are resting or engaged in emotion/cognition tasks and while cortical stimulation on and off. In addition to brain signals recordings, symptoms will be assessed using validated questionnaires and tasks to allow identification of neurophysiological correlates of non-motor symptoms. These signals will be used to determine the optimal stimulation parameters to disrupt symptom-related neural activity, and to implement feedback-controlled cortical stimulation
 
Hypotheses:
 
 
1) Characteristics of the prefrontal ECoG potentials (spectral power in specific bands, interaction between different frequency bands and/or between brain regions) correlate with severity of non-motor symptoms
 

	
2) For patients who have non-motor fluctuations in mood, anxiety, or impulsivity in response to dopaminergic medication, characteristics of the prefrontal ECoG potentials will vary in relation to medication state.
 
3) Cortical stimulation can reduce the severity of non-motor symptoms
 
4) Patients can learn how to voluntarily modulate cortical signals related to non-motor symptoms

Patient Population	Study subjects will be adults with Parkinson's disease (PD) deemed appropriate candidates for the treatment of motor symptoms using deep brain stimulation. Study subjects will also have one or more of the following non-motor symptoms: depression, anxiety, or impulsive behavior.
Sample Size	10 subjects

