*Study visits:* Phase I consists of eleven study visits (**Table 2**). Eight occur during defined time points that coincide with normal clinical care visits (preoperative, day of surgery, day after surgery, 10 days, 4 weeks after surgery, 2-4-6-months after surgery), with four additional research visits (3 weeks and 3-5-7 months

after surgery). In Phase 2, ten study visits will take place (12 months to 60 months post-implantation), five of them coincide with clinical car visits. Some of the out-patient study visits require that PD patients stop their oral levodopa 12 hours prior to the visit which is frequently done for clinical assessment purposes, as well as research studies.

In addition, patients might be offered to participate in an optional minimally invasive sleep study that aims to understand how sleep might alter brain waves. During this sleep study, physiological signals, including brain signals, oxygen level, heart rate, breathing, eye and body movements, will be recorded overnight. Recordings will be done at the UCSF sleep laboratory at least 12 months after the DBS surgery. Additionally patients will stream neural data overnight using the RCS device at home with a paired wearable watch. During this sleep study patients will be on their regular medication dose. Understanding brain waves modulations during sleep in individual subjects is a crucial step in developing closed loop stimulation algorithms that might be used chronically.

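### After implantation the "off medication" brain recordings are timed to low mood, so the on/off contrast for Hypothesis 2 can create or exaggerate a difference that is not a medication effect

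*Combined protocol and SAP*

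**What the plan says.** The paragraph on medication state in section 6.0 (Study Procedure) begins with an exposure rule: "The off medication state is defined as 12 hours off all anti-Parkinsonian medications". The same sentence limits that rule and then replaces it: "at baseline (prior surgery) then will be tailor to capture patient's low mood state". No minimum interval and no list of drugs applies afterwards. The on state keeps a dose-and-clock rule: "The on medication state is defined as 30-60 minutes after normal or" a suprathreshold dose. The order of the on and off recordings at visits 2 to 6 is left to symptoms and comfort, and at later visits the choice of medication state is left to symptoms.

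Table 2 gives the purpose of the on/off recordings at visits 2 to 6 as studying what antiparkinsonian medication does to brain signals and symptoms. Section 9.0 enters this as a factor in a repeated measures ANOVA, comparing "different medication states (on and off), in a repeated measures (within subjects) design". Hypothesis 2 in the Synopsis, limited to patients whose non-motor symptoms fluctuate with dopaminergic medication, is that "characteristics of the prefrontal ECoG potentials will vary in relation to medication state". Hypothesis 1 expects the same signals to correlate with symptom severity, and section 3.0 accepts that symptoms may fluctuate spontaneously as well as with treatment.

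Elsewhere in section 6.0, under study visits, some outpatient visits are said to require that "PD patients stop their oral levodopa 12 hours prior to the visit". That names one drug, where the medication-state paragraph refers to all anti-Parkinsonian drugs.

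**The concern.** A medication factor should have levels defined by drug exposure. Here one level (on) is, and the other (off), for every recording made with the implanted device, is steered by mood. Mood is what the signal is expected to follow. If the off recording is taken when mood is low, a symptom difference between the two levels is built in, and a signal difference follows for any marker that tracks mood. Section 9.0 names no adjustment for time since dose, mood at recording, or order.

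At stake is what Hypothesis 2 can tell the investigators: a reported on/off difference could be a medication effect, a mood-selection effect, or a mixture, with no means of separating them unless dose times are kept. The low-mood sampling itself is sensible for finding a biomarker; the difficulty is using the same label for the medication question.

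**Working it through.** **Nothing to reproduce.** The plan gives no alpha, power, effect size or sample-size calculation for this contrast, so its size has to be explored under stated assumptions.

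**From the documents:** 10 patients; on and off recordings at visits 2 to 6, so 5 visits; a within-patient on/off comparison.

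**Assumed:** two-sided 5% test; within-patient mood and signal standardised to SD 1, low values meaning low mood; mood-signal correlation r = 0.3 or 0.5; the off recording taken at the lowest of k candidate moods; the on recording unselected; no drug effect on mood or signal; correlation c between moods within a visit (the on mood included) of 0 or 0.7. The test is a one-sample t-test on the 10 patient-mean differences, equivalent to the ANOVA main effect of medication with 1 and 9 df.

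**Spurious difference.** Expected on-minus-off signal difference = r × √(1 − c) × E(k), where E(k) is the expected distance of the lowest of k independent standard normal values below the mean: E(2) = 0.565, E(3) = 0.846. For k = 3:

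- c = 0: 0.3 × 0.846 = 0.25 SD; 0.5 × 0.846 = 0.42 SD.
- c = 0.7: √0.3 = 0.548, so 0.3 × 0.548 × 0.846 = 0.14 SD; 0.5 × 0.548 × 0.846 = 0.23 SD.

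**False-positive rate** (Monte Carlo, 20,000 simulated studies per cell, rounded):

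| Candidate moods k | Within-visit mood correlation c | r = 0.3 | r = 0.5 |
|---|---|---|---|
| 1 (no selection) | 0 | 5% | 5% |
| 2 | 0 | 12% | 25% |
| 3 | 0 | 21% | 49% |
| 2 | 0.7 | 7–8% | 12% |
| 3 | 0.7 | 10% | 21% |

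At r = 0 there is no inflation whatever k is: selection on mood harms the signal contrast only if the signal tracks mood, which is Hypothesis 1.

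**If the drug does work.** When all candidate off moods are shifted by the same drug effect, selection adds the same quantity to the true difference. At k = 3 and r = 0.3 that is 0.14 to 0.25 SD on top of whatever the drug does. This is exaggeration rather than invention.

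**The levodopa-only sentence, taken separately.** Suppose the full on/off effect is 0.6 SD, with no mood selection and independent recordings. The SD of one visit's difference is √2, the SD of a patient mean over 5 visits is √(2/5) = 0.632, and the standard error over 10 patients is 0.632/√10 = 0.20. The standardised effect is 0.6/0.20 = 3.0, with power 75.6%. If withholding one drug removes only 75% or 50% of the effect, this becomes 0.45/0.20 = 2.25 (power 51.8%) or 0.30/0.20 = 1.5 (27.0%). With no effect at all the rejection rate is 5.2%, so this route dilutes and does not create a difference.

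**The case against.** Several points on the other side are fair, and they limit how far the concern goes.

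- *Tailoring may mean adjusting the length of withdrawal, not dropping it.* This is a possible reading, and Table 2 still lists visits 2 to 6 as off and on medication. A reader might infer that any low-mood recording counts as off whatever the drug exposure; the text does not say so. What stands is that no minimum interval is set, so timing, and with it the label, can still depend on mood.
- *Hypothesis 2 covers only patients whose symptoms respond to dopaminergic medication.* Correct. A reader might infer that any marker satisfying Hypothesis 1 would satisfy Hypothesis 2 with no drug effect at all. In the stated population a mood-tracking marker should truly differ by medication state, so exaggeration is the likelier harm. That group may also number fewer than 10, because on/off fluctuation is only one of the qualifying symptom criteria; rejection rates would then be lower, but the bias in the difference would remain.
- *The selection model is invented.* The documents describe no step of watching k moods and taking the lowest, and moods hours apart are unlikely to be independent. That is why the correlated case is shown; it roughly halves the rates at k = 3. If the interval were fixed in advance without regard to mood at the session, there would be no inflation under a null drug effect.
- *Baseline and later recordings.* A reader might infer that off brain recordings made under two definitions are pooled. They cannot be: no implanted-device recording exists before surgery. Only symptom ratings could be mixed. The 12-hour off state for the UPDRS part III at the one- and two-year visits is also untouched by this point.
- *The levodopa sentence.* A reader might take it as a rival definition that helps to produce false differences. It describes visit preparation, labels no recording as off, and works in the opposite direction.
- *The study is an exploratory pilot.* True. No error rate is controlled, and none of the three success criteria in section 9.0 uses the on/off medication contrast.

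**Conclusion.** The concern holds for brain recordings after implantation. The off level is steered by low mood with no minimum time off drug, the on level by dose and time, and the plan then reads the contrast as a medication effect. This can create an on/off difference and, in the patients whom Hypothesis 2 addresses, more plausibly exaggerate one.

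The size cannot be taken from the documents. For the lowest of 3 moods it ranges from about 10% to 49% false positives against a nominal 5%, or 0.14 to 0.42 SD of spurious difference, depending on the assumed mood-signal correlation (0.3 to 0.5) and within-visit mood correlation (0 to 0.7). These figures illustrate a direction and a plausible scale; they do not predict what this study will find.

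The mismatch between levodopa alone and all anti-Parkinsonian drugs is a separate inconsistency, whose effect is a heterogeneous off state and possible dilution. The harm overall is to the interpretation of Hypothesis 2, not to a confirmatory test. It is worth correcting because dose times not captured at the session may not be recoverable later.

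**What to change.** 1. Reconcile the two passages in section 6.0 on which drugs are withheld and what off means. Which withdrawal rule applies is for the investigators; no change to any patient's medication or withdrawal is proposed here.
2. At every brain recording, log the time since last dose of each anti-Parkinsonian drug.
3. In section 9.0, derive the medication factor for Hypothesis 2 from that logged exposure, by one definition at all visits, and not from mood. Alternatively, use time since last dose as the predictor in the mixed model that section 9.0 already allows.
4. Flag recordings timed to low mood. Use them for the symptom-signal analysis, and report the Hypothesis 2 contrast with and without them. Where too few exposure-defined recordings remain, describe the result as a mood-state contrast.

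Excluding every mood-timed recording outright is not advised: all post-implant off recordings fall under the tailored wording, so exclusion could empty the contrast. Adjusting for mood alone would not do either, since it changes the question to the drug effect at a given mood.

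The cost is protocol wording, one added set of dose-time entries per session, and possibly few off recordings that qualify for Hypothesis 2.
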